RESEARCH PROTOCOL

Single lung ventilation refers to the situation in which one lung is ventilated and the other lung is deflated, mechanically separating the two lobes of the lung. Single lung ventilation is performed to facilitate surgical access in intrathoracic procedures involving the lung, esophagus, anterior mediastinal structures, and aorta, as well as in selected orthopedic spine procedures (1). There are three types of lung isolation methods; 1. Double-lumen endobronchial tube, 2. Broach blocker, 3. Single-lumen endobronchial tube (2). The most commonly used method for single-lung ventilation is intubation with a double-lumen endobronchial tube (3), (4). Double-lumen tubes allow isolation of both lungs, selective ventilation, and intermittent suctioning. A double-lumen tube has separate tracheal and bronchial lumens; it is essentially two tubes connected side by side. The shorter tube has a high-volume, low-pressure tracheal head and forms the tracheal lumen positioned just above the carina. In both left and right double-lumen tubes, the smaller, low-volume, high-pressure bronchial cuff is ideally positioned just below the tracheal carina and before the division of the lobar bronchus. The cuffs pilot balloons and the connection areas at the top of each of the two tubes are all color-coded (white for the tracheal tube and blue for the endobronchial tube). When the double-lumen tubes are properly positioned, both the tracheal and bronchial cuffs are inflated, clamping the lumen of the opposite lung to provide selective single-lung ventilation. Left double-lumen tubes are most often selected because of the longer left main bronchus, easier positioning, and greater margin of error compared to right double-lumen tubes. The length of the left bronchus is 4-6 cm in men and 3-5 cm in women, while the length of the right main bronchus is 1-2 cm. It is more difficult to maintain the position of right double-lumen tubes than left double-lumen tubes, therefore complications due to incorrect positioning may be more common. For these reasons, the use of right double-lumen tubes is limited to special situations. These are; left pneumonectomy, distorted anatomy of the left main bronchus entrance due to external and intraluminal compression, and the surgical site containing the left main bronchus. Placement of left double-lumen tubes is generally easier than right double-lumen tubes. Under direct laryngoscopy, the endobronchial tip is inserted between the vocal cords, the stylet is removed, and the double-lumen tube is rotated 90 degrees to the left while advancing. Airway damage (hoarseness, sore throat, tracheal rupture) and hypoxemia may occur due to incorrect positioning of the double-lumen tube (5). Traditionally, the position of the left double-lumen tube is confirmed by auscultation. Initial auscultation is performed with both tracheal and bronchial cuffs inflated; if the double-lumen tube is properly inserted, ventilation through both lumens should result in equal bilateral breath sounds. The tracheal lumen is then clamped and ventilation should result in breath sounds on the left side but not the right. The bronchial lumen is then clamped and ventilation should result in breath sounds on the right side but not the left. Fiberoptic bronchoscopy is the gold standard for confirming the position of double-lumen tubes (6). If the left double-lumen tube is ideally positioned, the initial bronchoscopic view through the tracheal lumen will show a blue bronchial balloon visible just beyond the carina on the left side without herniation into the trachea. The tube is then confirmed by advancing the bronchoscope into the bronchial lumen to ensure that the bronchial tube has not been advanced too far. The video double lumen tube, which has been used in recent years, is a technique where the tube location can be continuously seen on the screen during the application and surgery, but it has not become very widespread yet (7), (8). The primary purpose of this study is to investigate the superiority, advantages and disadvantages of these techniques used for the correct and short-term positioning of the double lumen tube in single lung ventilation. The secondary purpose is to determine the method that will ensure that the tube location can be verified in the shortest time and that intraoperative location changes can be detected in a short time, and that complications that may occur due to incorrect placement of the double lumen tube can be prevented, thus reducing complications. Other purposes are to perform the intubation procedure with the double lumen tube in the shortest time and verify its location in the shortest time, to save time, to prevent complications by detecting tube location changes in the intraoperative period in the shortest time, and thus to provide the shortest and safest operation time. Shortening the duration and preventing complications will also reduce costs. Although it has been stated in the literature that video double

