In Kayseri City Hospital, ASA I-III patients aged 18-84 who are planned to undergo surgery with single lung ventilation between December 2024 and May 2025 will be included in the study after obtaining their informed consent. In our hospital, video double lumen tube verification techniques, and auscultation and fiberoptic bronchoscopy are routinely used for conventional double lumen tubes. Patients are blinded in terms of the method to be applied, and since the anesthesiologist who will perform the intubation procedure is the person who performs the method, blinding cannot be performed. Anesthesiologists who perform the intubation procedure will not have any information about the study. They will use the method they prefer. Patient randomization will be done in this way. In the study, volunteers were blinded because they did not know which intubation method would be used, while blinding could not be done for the anesthesiologist who would perform the intubation. Due to the advantages mentioned above, a left tube will be used in all patients. Tube sizes will be determined according to the height and gender of the patients. Group I will be divided into three groups randomly as patients whose tube location will be confirmed by auscultation, Group II patients whose tube location will be confirmed by using fiberoptic bronchoscopy, and Group III patients whose tube location will be confirmed by using a video-guided double-lumen intubation tube. After the patients are taken to the operating room, routine monitoring will be applied and vascular access will be established with an 18G intravenous catheter. After preoxygenation with 100% O₂ for 2 minutes, anesthesia induction will be applied with 2-3 mg/kg propofol, 1-2 mcg/kg fentanyl, and 0.6mg/kg rocuronium. They will be ventilated with 100% oxygen until neuromuscular blockade occurs for at least 2 minutes. The intubation duration will be started after the vocal cords are visualized with the laryngoscope and will be taken as the time until end tidal CO₂ is seen on the monitor. Intubation verification time was planned for Group I as the time when bilateral respiratory sounds are heard while both cuffs are inflated, then the tracheal lumen is clamped and no respiratory sounds are heard on the right, respiratory sounds are heard on the left and then the bronchial lumen is clamped and no respiratory sounds are heard in the left lung, and respiratory sounds are confirmed to be heard in the right lung. For Group II, it was planned to be taken as the time when the fiberoptic bronchoscope is first entered into the tracheal lumen and the carina and bronchial blue-colored cuff is seen to be inflated without herniation in the left bronchus and then entered through the left bronchial lumen and it is seen that the tube is not advanced too much. III. In the group, it was planned to be taken as the time when the bronchial lumen of the video double lumen tube entered the left bronchus and the blue cuff was inflated. After the patients were given the lateral decubitus position with the lung to be operated on top, the tube location for each group was confirmed again and the time was recorded. Anesthesia maintenance will be provided using 1 MAC sevoflurane. The number of intubation attempts in the 3 groups, the duration of intubation, the duration of tube location verification, the quality of lung collapse, the need for fiberoptic bronchoscopy, the duration of fiberoptic bronchoscopy, the number of tube dislocations, and the duration of dislocation correction will be monitored. After extubation, the patients will be taken to the recovery room. In the recovery room, the patients will be questioned about the presence of sore throat and hoarseness. The methods used in the patients will be compared in terms of cost according to the type of tube and the use of fiberoptic. The data to be collected for the study will be recorded using the SPSS 22 program and analyzed in the same program. Frequency, percentage, mean value, standard deviation, maximum and minimum (min-max) values will be used for descriptive statistics, Pearson Chi-square test will be applied for statistical analysis of categorical data and Fisher's Exact Test will be applied for values below five in four-sided tables.

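### The number of tube dislocations is compared across groups with no definition and unequal means of detection, so a higher count in the video group cannot be read as more dislocation

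*Protocol*

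**What the plan says.** The outcomes list in the protocol's methods text states that "the number of tube dislocations, and the duration of dislocation correction will be monitored". Neither document defines a dislocation, names who judges it, or sets a schedule for looking for one.

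The means of seeing the tube differ by group:

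- **Group I:** "patients whose tube location will be confirmed by auscultation".
- **Group II:** "Group II patients whose tube location will be confirmed by using fiberoptic bronchoscopy".
- **Group III:** uses the video tube. The protocol's background says that with this device "the tube location can be continuously seen on the screen during the application and surgery".

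After initial verification, one further check is described for everyone. Once the patient is in the lateral position, "the tube location for each group was confirmed again and the time was recorded". No later check is scheduled in any group.

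The background also states that "Fiberoptic bronchoscopy is the gold standard for confirming the position of double-lumen tubes", yet bronchoscopy is not scheduled as a common check. Instead, "the need for fiberoptic bronchoscopy, the duration of fiberoptic bronchoscopy" appear among the outcomes, with no stated trigger. A secondary purpose is that "intraoperative location changes can be detected in a short time".

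The SAP gives general tests: chi-square or Fisher for categorical data, and ANOVA, t test, Kruskal-Wallis or Mann-Whitney for quantitative data. It makes no allowance for differing detection.

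**The concern.** A recorded dislocation is one that occurred and was noticed. From lateral positioning to the end of surgery, Group III has a view of the tube available at all times, while Groups I and II have no planned look. If tubes move equally often in all three groups, the recorded counts can still differ.

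The natural reading of a dislocation count is that more is worse. On that reading, a method that shows more of the movement could be marked down for showing it, which would run against the study's aim of reducing complications from tube displacement. Correction time has a related problem: it exists only for detected events, and the mix of events detected may differ by group.

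**Working it through.** **1. The plan's own figure.** The protocol gives a total of 93 for three groups, from an effect size of 0.33, 95% confidence and 80% power. Taking 0.33 as Cohen's f in a one-way ANOVA with noncentrality N × f², the minimum total is 92. That becomes 93 with three equal groups of 31, where power is 80.7%. The figure reproduces. It bears on this point only by supplying 31 per group, since the protocol does not state the group sizes.

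**2. Surveillance by period, from the documents.**

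| Period | Group I | Group II | Group III |
|---|---|---|---|
| After intubation | auscultation | bronchoscopy | video view |
| After lateral positioning | re-check, own method | re-check, own method | re-check, own method |
| Rest of surgery | nothing scheduled | nothing scheduled | nothing scheduled, but view available |

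The re-check is common in timing but not in method. In the last period even the opportunity to see a shift differs.

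**3. Illustration of size.** The documents give neither a dislocation rate nor a detection rate, so both are assumed here. Let p be the true proportion of patients with at least one dislocation, equal in all groups, and let d be the probability that it is detected. The recorded proportion is p × d. With 31 per group, the expected number recorded is 31 × p × d. At p = 40%:

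- d = 50%: 31 × 0.40 × 0.50 = 6.2
- d = 70%: 31 × 0.40 × 0.70 = 8.7
- d = 100%: 31 × 0.40 × 1.00 = 12.4

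The probability that a 3x2 Pearson chi-square test rejects at 0.05 was found by enumerating all outcomes of three independent binomials. Because true rates are equal, every rejection is false as a statement about tube movement.

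| Detection I/II/III | p = 10% | p = 20% | p = 30% | p = 40% |
|---|---|---|---|---|
| 100/100/100% | 4.1% | 5.0% | 5.0% | 4.8% |
| 90/95/100% | 4.1% | 5.3% | 5.5% | 5.6% |
| 70/80/100% | 4.9% | 8.1% | 10.4% | 13.4% |
| 50/70/100% | 7.1% | 14.9% | 22.8% | 32.2% |

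At p = 5%, the last two rows give 4.1% and 5.0%.

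**4. If the outcome is kept as a count.** The SAP would send a count to the quantitative tests. A simulation used Poisson counts with equal true means of 0.3 to 1.0 per patient, full detection in Group III, and a common detection probability s in Groups I and II. Kruskal-Wallis rejected in 6% to 11% of trials at s = 0.8, 13% to 37% at s = 0.6, and 23% to 59% at s = 0.5. At s = 1 it stayed near 5%. The apparent ratio of Group III to the others is 1/s: 1.25, 1.67 and 2.0.

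**5. Check on a tempting remedy.** One could exclude events seen only on screen and keep events revealed by a clinical sign in every group. But a shift seen and corrected early in Group III may never produce a sign, while the same shift in Groups I or II may go on to produce one. With detection of 50% and 70% in Groups I and II, and an assumed 20% of Group III events still counted, false rejection is 17%, 31% and 44% at p = 20%, 30% and 40%. That exceeds the 15%, 23% and 32% of the raw comparison, and it now favours the video tube.

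**The case against.** The strongest reply is that detection is part of what is being studied. Prompt detection of location changes is a stated purpose, so a video tube that reveals more of them is doing its job. This stands as a reason to report detection, but not as a reason to read one total as the rate of displacement: a high count in Group III could mean more movement or more movement seen.

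Other objections hold in part:

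- The illustration rests on assumed rates. At true rates of 5% to 10%, or with detection of 90/95/100%, the error rate stays at about 4% to 7%.
- The chi-square figures need the count reduced to yes/no, which neither document does. The Kruskal-Wallis figures show that the problem does not depend on that choice.
- Dislocation is one of several monitored items, and none is named as primary.
- Anesthesiologists use the method they prefer, so group comparisons are open to confounding by operator choice whatever is done about detection.

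A reader might infer that Group III is actively watched throughout, and that dislocations in Groups I and II come to light only on suspicion. The documents support neither. The background says that the video position can be seen, not that anyone is assigned to watch it. For Groups I and II, the text is silent on how later dislocations are found. Nor do the documents show that the video group will record more dislocations: that follows only if true rates are similar and the view is used.

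**Conclusion.** The point holds as a limit on interpretation. The plan compares a dislocation count across groups whose means of finding a dislocation differ by design, with no definition, common assessment or record of detection mode to separate movement from visibility. A higher count in Group III cannot be read as more dislocation, and correction times carry the same selection.

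The size cannot be computed from the documents. Under the assumptions above (equal true rates, 31 per group, any dislocation yes/no), false rejection is 15/23/32% with detection of 50/70/100% and 8/10/13% with 70/80/100%, at true rates of 20/30/40%. At a 10% rate it is 7% or 5%. It is near nominal when detection is nearly equal. The change should be made before data collection, because how an event was found may not be recoverable afterwards.

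**What to change.** 1. Define a tube dislocation in writing, in the same terms for all groups.
2. For each event, record the time and how it was found: scheduled lateral re-check, clinical or surgical sign, screen view, or bronchoscopy.
3. In the SAP, limit the formal between-group comparison to tube position at the lateral re-check, which all groups have at the same point. State that the checking method still differs by group.
4. Report later events, and their correction times, descriptively by mode of detection in all groups. Do not drop screen-only events from Group III alone.
5. State that the total count will not be interpreted as a dislocation or complication rate.

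The cost is two fields on the data form, a definition, and a few sentences in the SAP. No change to patient care is needed. The formal comparison will have fewer events, and some detection bias remains at the re-check because the three methods differ. Confounding by operator choice of method is a separate matter that this change does not address.

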
RESEARCH PROTOCOL

lumen tubes are cost effective, their superiority over other techniques has not been demonstrated because their use has not yet become widespread. Another aim of the study is to compare the cost effects of these three methods.

Using the studies in the literature, the total number of patients for three groups was found to be 93 by using G-power to calculate the sample size and taking the effect size as 0.33 at a 95% confidence level and 80% power.

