
RESEARCH PROTOCOL

The conformity of quantitative data to normal distribution will be tested with the Kolmogorov-Smirnov and Shapiro Wilk tests. For statistical analysis of quantitative data in independent groups, Unpaired t test and One-Way Anova test (post hoc Tukey test) will be used for data conforming to normal distribution, Mann-Whitney U, Kruskall-Wallis test and Pearson Correlation coefficient will be used to show the relationship between variables for data not conforming to normal distribution. Statistical significance of the difference was accepted as p<0.05.

SOURCES:

1. Mehrotra, M. and A. Jain, Single-Lung Ventilation, in StatPearls [Internet]. 2023, StatPearls Publishing.
2. Hickey, S.M. and A.O.J.T.I.S.P. Giwa, Mechanical ventilation. 2020.
3. Morgan, G. and M.J.K.A. Mikhail, MurrayMJ. 2002: p. 1040-2.
4. Campos JH. Current techniques for perioperative lung isolation in adults. *Anesthesiology*. 2002; 97:1295–1301.
5. Liu, S., Y. Mao, P. Qiu, et al., Airway rupture caused by double-lumen tubes: A review of 187 cases. 2020. 131(5): p. 1485-1490.
6. Campos JH. Which device should be considered the best for lung isolation: double-lumen endotracheal tube versus bronchial blockers. *Current Opinion in Anesthesiology*2007
8. The Video Double-Lumen Endobronchial Tube: Is the Benefit Worth the Cost? *Journal of Cardiothoracic and Vascular Anesthesia* 32 (2018) 275–276

RESPONSIBLE RESEARCHER: Doc. Dr. [name]

ASSISTANT RESEARCHER: [name] [name]

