STATISTICAL ANALYSIS

The data to be collected for the study will be recorded using SPSS 22 program and analyzed in the same program. Frequency, percentage, mean value, standard deviation, maximum and minimum (min-max) values will be used for descriptive statistics, Pearson Chi square test will be applied for statistical analysis of categorical data and Fisher's Exact Test will be applied for values below five in four-sided tables. The conformity of quantitative data to normal distribution will be tested with Kolmogorov-Smirnov and Shapiro Wilk tests. For statistical analysis of quantitative data in independent groups, Unpaired t test and One-Way Anova test (post hoc Tukey test) will be used for data conforming to normal distribution, Mann-Whitney U, Kruskall-Wallis test will be used for data not conforming to normal distribution and Pearson Correlation coefficient will be used to show the relationship between variables. Statistical significance of the difference was accepted as $p < 0.05$.

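### Correction time exists only where a dislocation was detected, and detection differs by group, so testing it compares method-selected subsets with bias of unknown direction

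*Protocol*

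**What the plan says.** The Protocol's methods text lists eight items to be followed in the three groups, ending with "the number of tube dislocations, and the duration of dislocation correction will be monitored". The item at issue is the last, "the duration of dislocation correction". Neither document defines a dislocation, says how one is to be found in each group, says when the correction clock starts and stops, or says how a patient without a dislocation enters the analysis.

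The groups are defined by how tube position is checked: by listening (Group I), by fiberoptic bronchoscopy (Group II), or by a video tube (Group III). The Protocol's introduction says the video tube's position can be watched throughout surgery. Position is rechecked in every group after the patient is turned, but no common reference check is described. Bronchoscopy is called the reference technique in the introduction and is not stated to be applied to everyone.

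The SAP's Statistical Analysis text has one rule, introduced by "For statistical analysis of quantitative data in independent groups": t test or ANOVA if the data look normal, Mann-Whitney or Kruskal-Wallis if not. The Protocol's statistical paragraph gives the same tests. No outcome is named primary, and no separate rule covers an outcome that exists only after an event.

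**The concern.** Correction time is recorded after two things have happened: the tube moved, and someone noticed. The second depends on the method under study. A group with a more sensitive check contributes dislocations that another group would have missed, so the patients compared are no longer the allocated groups but whichever members of them each method picked out. This would be so even with sound randomization. Here allocation follows the anesthesiologist's choice ("They will use the method they prefer. Patient randomization will be done in this way"), which is a separate and larger problem.

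At stake is a p-value that looks like a difference in how fast the methods put a displaced tube right, when it may reflect only which displacements each method noticed. It bears on one of the Protocol's stated aims, the quick detection of position changes during surgery. The comparison also rests on a fraction of the patients.

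**Working it through.** **1. The plan's own figure.** The Protocol states that "the total number of patients for three groups was found to be 93", "taking the effect size as 0.33 at a 95% confidence level and 80% power", with significance at p < 0.05. Reading 0.33 as Cohen's f for a one-way ANOVA in three groups (the Protocol names neither test nor outcome), the noncentrality is f² × N = 0.1089 × 93 = 10.13. Power is 0.807. The smallest N reaching 80% is 92, or 93 in equal groups, so 93 reproduces. It applies to an outcome measured in every patient.

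**2. How many patients carry a correction time.** The documents give no dislocation rate, so this is a range. If 10%, 20%, 30%, 40% or 50% of the 93 have a detected dislocation, about 9, 19, 28, 37 or 46 patients have a value. Power at f = 0.33 is then about 10%, 20%, 29%, 39% or 48%. The effect size is not stated to be for this outcome; the figures only show scale.

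**3. Bias with no true method effect.** Assumptions, none from the documents: 31 patients per group (no allocation ratio is stated), a true dislocation rate of 40% in each group, and severity s exponential with mean 1. A dislocation is detected when s is at least t, with t = 0.7, 0.35 and 0 for auscultation, bronchoscopy and video. The detected share is exp(−t): 0.50, 0.70 and 1.00. Correction time depends on s in the same way in all groups, plus noise with SD 10 s.

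- *Time rises with severity*, 20 + 60s seconds. The mean of s given s ≥ t is 1 + t, so the expected means are 20 + 60 × 1.70 = 122 s, 20 + 60 × 1.35 = 101 s and 20 + 60 × 1 = 80 s.
- *Time unrelated to severity*, mean 80 s. All groups are expected at 80 s (simulated: 81, 80, 80).
- *Time falls with severity*, 20 + 60 exp(−s) seconds. The mean of exp(−s) given s ≥ t is exp(−t)/2, so the expected means are 20 + 30 × 0.497 = 35 s, 20 + 30 × 0.705 = 41 s and 20 + 30 × 1 = 50 s.

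False rejection by Kruskal-Wallis at 5%, by simulation, among detected cases (trials with fewer than two such cases in a group left out):

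| Link of time to severity | Means, auscultation / bronchoscopy / video | False rejection | Video looks |
|---|---|---|---|
| Rises | 122 / 101 / 80 s | about 30% | best |
| Unrelated | 80 / 80 / 80 s | about 5% | the same |
| Falls | 35 / 41 / 50 s | about 24% | worst |

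**4. A different model.** With lognormal severity and detection of 40%, 70% and 100%, the means in the same order were 59.7, 46.7 and 37.6 s (rising), 31.4 s in each group (unrelated), and 18.5, 25.2 and 37.5 s (falling). False rejection was about 29%, 4% and 30%. The pattern is the same.

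**5. The companion count.** Under step 3, each group truly has 31 × 0.40 = 12.4 dislocations. The detected numbers are 12.4 × 0.497 = 6.2, 12.4 × 0.705 = 8.7 and 12.4. The most sensitive detector shows the most dislocations although the true rates are equal, so the detected rate is not a like-for-like comparison either.

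**The case against.** The strongest reply is about weight. Correction time is one of eight monitored items, is not named primary and is not tied to the sample size. Neither document singles it out for testing; that follows only from the general rule for quantitative data. The number of dislocations is collected, so a careful reader could set one beside the other. Preference-based allocation already makes every comparison doubtful. All of this stands and limits the point to a secondary item. It does not remove it, because the general rule as written covers this outcome and no caution is attached.

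A reader might go further and infer that the comparison favours the video tube, since continuous viewing should add small displacements that are quick to put right. The documents do not support that. They do not say that correction time rises with severity, that missed dislocations are the quick ones, or what share each method detects. The first row of the table depends on the rising link built into it; the other two rows show no bias and the opposite bias. Direction also depends on whether the clock starts at displacement or at detection, which is undefined.

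A reader might also propose analysing total correction time over all patients, with zero where none was needed. If each group's own detections are used, this falsely rejects in roughly 14% to 42% of trials across the scenarios considered. If only dislocations detectable in every group are counted, false rejection is controlled, but in the rising model a true halving of video correction time is found in only 4% to 5% of trials at dislocation rates of 20% to 40%, because tied zeros dominate the ranks. It would also need a common position check, which the Protocol does not describe.

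**Conclusion.** The point holds for a secondary item. As planned, the test of correction time compares subsets formed after allocation by the methods being compared, and a significant result could not be read as an effect of method on correction time. Under the assumed 40% dislocation rate and 50%/70%/100% detection, the false-rejection rate lies between about 5% and about 30%, and the group that appears better depends on a link between severity and correction time that the documents do not give. Those rates, detection shares and severity models are illustrations, not estimates for this trial. What rests on the documents alone is that the outcome requires detection, that the means of detection differ by group, and that no analysis set or handling rule is stated.

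**What to change.** In the SAP, take this outcome out of the general testing rule and report it as descriptive only: for each group, the number of corrected events and the median and range of correction time per corrected event, with no between-group p-value and no claim of superiority. Beside it, give the number and proportion of all patients in the group with a detected dislocation. Add a sentence that detection differs by method, so neither the correction times nor the detected-dislocation rates are a like-for-like comparison. The Protocol's statistical paragraph carries the same general rule and needs the same exception.

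The cost is that one secondary item loses its formal test. No additional position check is needed.

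### Sore throat and hoarseness are asked about only after surgery, so symptoms already present cannot be told apart from new ones and could be counted as complications of the tube-verification method

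*Protocol*

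**What the plan says.** - **Who enters.** The protocol's methods paragraph states eligibility as "ASA I-III patients aged 18-84 who are planned to undergo surgery with single lung ventilation between December 2024 and May 2025 will be included", subject to informed consent. No exclusion criteria are listed, so a patient with an existing throat or voice complaint is eligible.
- **What is measured.** The same paragraph says "In the recovery room, the patients will be questioned about the presence of sore throat and hoarseness". The question concerns presence, not onset, and comes after extubation. Neither document describes a matching question before induction.
- **How the symptoms are interpreted.** The protocol's background says "Airway damage (hoarseness, sore throat, tracheal rupture) and hypoxemia may occur due to incorrect positioning of the double-lumen tube". The secondary purpose includes that "complications that may occur due to incorrect placement of the double lumen tube can be prevented, thus reducing complications".
- **How groups are formed.** "They will use the method they prefer. Patient randomization will be done in this way".
- **How the outcome is compared.** The SAP says "Pearson Chi square test will be applied for statistical analysis of categorical data", with Fisher's exact test for small counts in two-by-two tables. It gives no new-onset definition and no adjustment for baseline status.

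**The concern.** A symptom counted as harm from a procedure should be absent before the procedure. Here a patient who is hoarse on arrival and one who becomes hoarse after intubation give the same answer in the recovery room.

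Two things can follow. If pre-existing symptoms are equally common in the three groups, they add the same background to each and dilute any true difference. If they are unequally common, they can produce a difference where the methods do not differ. Equal frequency cannot be assumed, because the anesthesiologist chooses the method. What is at stake is the interpretation of the only patient-reported outcome in the plan, which bears on the secondary aim of fewer complications.

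**Working it through.** **1. The plan's own figure.** The protocol gives 93 patients in three groups, "taking the effect size as 0.33 at a 95% confidence level and 80% power". Read as a one-way ANOVA with Cohen's f = 0.33, the noncentrality is N × f². At N = 93 this is 93 × 0.1089 = 10.13 and power is 0.807. At N = 90 it is 9.80 and power is 0.793. The smallest balanced total is therefore 93, and the stated figure reproduces. It apparently was not based on a symptom rate.

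**2. Inputs for the symptom outcome.**
- From the documents: 93 patients, three groups, Pearson chi-square, significance at 0.05.
- Assumed: 31 per group (93/3; the allocation ratio is not stated), and all symptom rates, since neither document gives any. Let b be the proportion symptomatic before induction and q the new-onset rate among the rest.

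**3. Formulas.** Recorded rate = b + (1 − b) × q. Share of recorded cases that are pre-existing = b / [b + (1 − b) × q].

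For q between 30% and 20%, that share is 15–21% at b = 5%, 27–36% at b = 10% and 45–56% at b = 20%. Example: 0.10 / (0.10 + 0.90 × 0.20) = 0.10 / 0.28 = 36%.

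**4. Equal pre-existing rates, true new onset 10/10/40%.** Rejection rates of the three-group chi-square were simulated. The last column analyses new onset only, among patients free of symptoms at baseline.

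| b | Recorded rates | Power as written | Power, new onset only |
|---|---|---|---|
| 0% | 10 / 10 / 40% | 86% | 86% |
| 5% | 14.5 / 14.5 / 43% | 77% | 84% |
| 10% | 19 / 19 / 46% | 68% | 82% |
| 20% | 28 / 28 / 52% | 51% | 77% |

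The fair comparison is between the last two columns, because the remedy also loses some denominator. The recoverable power is about 7, 14 to 15 and 26 points. The drop from the symptom-free 86% is larger (9, 18 and 35 points from the rounded figures), but part of it is not recoverable.

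**5. Unequal pre-existing rates, no true difference (q = 25% in every group).** A group with b = 5% records 0.05 + 0.95 × 0.25 = 28.75%.

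| b by group | Recorded rate, third group | False positives as written | New onset only |
|---|---|---|---|
| 5 / 5 / 5% | 28.75% | 5% | 5% |
| 5 / 5 / 10% | 32.5% | 6% | 5% |
| 5 / 5 / 15% | 36.25% | 9% | 5% |
| 5 / 5 / 20% | 40% | 15% | 5% |
| 5 / 5 / 30% | 47.5% | 33% | 5% |

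The 5% in the last column depends on new onset being equally likely in all groups, which operator-chosen allocation does not guarantee.

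**The case against.** The strongest reply is that this is a minor outcome with a consequence of unknown size. Much of that stands.

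- **Scoring.** A reader might infer that the plan counts pre-existing symptoms as complications. The documents do not say so: there is no scoring rule and no definition of a complication. What they support is that such symptoms could be counted that way, since nothing separates old from new.
- **Irreparability.** A reader might also infer that baseline status is lost for good. The documents are silent on preoperative assessment, and silence in a short protocol does not show that no clinical record exists. A planned question would still be more uniform than a search of notes.
- **Frequency.** The surgical sites named in the background describe uses of single lung ventilation in general, not this hospital's case mix. No rate of pre-existing symptoms is given, and it may be low. At 2%, under the same 10/10/40% assumption, the remedy gains only about 2 to 3 points of power (83% to 85%).
- **False positives.** The alarming figures need a four- to six-fold imbalance. Nothing in the documents links existing hoarseness to the choice of method.
- **Allocation.** Choice by the operator confounds every outcome, and a baseline question does not correct that. The dilution in step 4, however, would remain even under proper randomization.
- **Importance.** The two symptoms are outside the protocol's list of monitored variables, and the timing and positioning outcomes are unaffected.

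None of this removes the gap: a single question after surgery cannot distinguish old symptoms from new in any population.

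**Conclusion.** The point holds as a measurement gap in a secondary outcome. Patients with existing sore throat or hoarseness may enter, only postoperative presence is planned to be recorded, and the background attributes these symptoms to malposition.

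The omission is clear from the text; its size is not. Under the assumed rates, analysing new onset would recover about 7 to 26 points of power for pre-existing prevalence of 5% to 20%. It would also remove a false-positive excess that is small under mild imbalance (6% to 9%) and substantial only under strong imbalance (15% to 33%). All of these figures rest on 31 per group and on symptom rates that the documents do not supply.

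The documents do not support reading this as an error in the sample size, which reproduces, or as a threat to the primary purpose. It is a cheap improvement, worth making before enrolment.

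**What to change.** 1. Ask the same two yes/no questions (sore throat, hoarseness) before induction, for example when consent is taken, and record the answers.
2. Define the outcome in both documents as new sore throat or new hoarseness: absent before induction, present in the recovery room.
3. Analyse each symptom among patients free of that symptom at baseline, and report baseline symptom rates by group.
4. Keep every patient for the timing outcomes.

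**Cost.** Two questions per patient and a sentence in each document; no treatment changes. The denominator for this outcome shrinks slightly: at 10% prevalence, from 31 to about 28 per group (31 × 0.90 = 27.9). Worsening of an existing symptom is not captured. Confounding from operator-chosen allocation remains and needs its own remedy.
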